## **1.a. Bone quality, demographics and hormonal status in hip fracture patients under 60 years of age.**

*First author:* [name]

*Co-authors:* (in random order) [name]; [name], [name], [name]; [name], [name]; [name].

*Last author:* [name]

*Study design:* Prospective multi-center cohort study

*Participants:* Approx. 200 individuals aged 18-60 years

*Exposure:* Acute, non-pathological hip fracture (intra- and extracapsular), regardless of trauma level

*Control group:* Cohorts of middle-aged, non-fractured individuals with DXA measurements at Odense and Skåne University Hospital

*Aim:*

1. Comparison of bone mineral density at the time of hip fracture (DXA scan) and basic risk factors for osteoporosis (BMI, smoking, etc. = variables accessible in the control groups)

Statistical analysis of categorical data using Chi-square test.

2. Descriptive analysis of other relevant factors in a young hip fracture cohort

Statistical analysis of categorical data using Chi-square test.

*Collected variables in the prospective study:*

Gender, age, BMI

Comorbidity, medication

Diet

Abuse – alcohol, drugs, tobacco, anabolic steroids

Socioeconomics (working capacity, type of living)

Fracture history (own and first-hand relatives)

Laboratory tests including hormonal status

DXA scan at the time of the fracture

Fracture pattern, type of trauma

Physical / functional level prefracture (New mobility score and others)

Health-related quality-of-life prefracture

*Hypotheses:*

There are differences in BMD and risk factors when comparing the hip fracture group with a standard control group.

Within the hip fracture group; different levels of BMD are associated with comorbidities, hormonal status and life style factors.

*Perspective/clinical relevance:*

To identify those patients who have an underlying cause or reason for sustaining a hip fracture in relatively young age and, when appropriate, initiate preventive measures for future fractures.

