Hip fractures can be divided into intracapsular and extracapsular fractures, the latter are treated with internal fixation in all patients. For intracapsular fractures, the patient's age determines the type of surgery. In "elderly", arthroplasty is the treatment of choice in displaced fractures, this can be either a total hip arthroplasty or a hemiarthroplasty. "Younger" patients are treated with internal fixation after fracture reduction. There is no consensus regarding which age limit should be used, and the assessment is complicated by the fact that "biological age" is more relevant than chronological age. In practical use, 60, 65 or 70 years are mostly used as the divide. Arthroplasty leads to fewer reoperations, and better pain relief and function (at least during the first years). Due to an assumed long life expectancy, internal fixation is used in younger individuals, as arthroplasty might lead to complications after 10-20 years. The short term risk of complications after internal fixation – 20-50% - is usually accepted, as these patients can tolerate secondary surgery with arthroplasty after failed fixation. The exact failure rate in younger patients is not known, and they may have better ability to heal their fracture than the geriatric population. Younger patients *may* have better bone quality, better blood supply to the femoral neck and head and better nutritional status, which all promotes fracture healing. On the other hand, we suspect hip fracture to be a sign of frailty, regardless of the patient's age.

Overall Aim:

The overall aim is to investigate the epidemiology of hip fractures in younger patients (regarding hormonal status, bone density and health profiles in comparison to a standard population), analyze of trauma and fracture type, fracture treatment and outcome as well as patient satisfaction during two years.

Material and Method:

The study is a prospective multi-center cohort study of young and middle-aged adults who have incurred a hip fracture; describing epidemiology of hip fracture in this age group, clinical results and

HFU-60

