patient reported outcome during two years following the hip fracture. Patients aged 18 to 59 years, who sustain an acute non-pathological hip fracture (defined by ICD-codes S72.00, S72.10 and S72.20) and are treated within four weeks at any of the participating hospitals, are invited to participate in the study. All patients are invited, regardless of medical, cognitive and functional pre-fracture status. The patients' informed consent is to be obtained before inclusion in the study.

Participating hospitals and approximate annual number of hip fractures in patients under 60 years:

- Skåne University Hospital (Malmö and Lund, Sweden) - 45
- Hvidovre Hospital (Copenhagen, Denmark) - 50
- Odense University Hospital (Odense and Svendborg, Denmark) - 50
- Kolding Hospital – part of Lillebælt Hospital (Kolding, Denmark) - 50

The projected number of included patients in the study is 200 to 300 individuals, which would require inclusion during one and a half to two years at all units, depending on the degree of patients accepting inclusion in the study. The study is mainly descriptive, wherefore power calculations are not considered feasible.

Patients are treated according to the department's standard rationale. In addition, the study will comprise interview and written enquires, blood tests regarding medical, hormonal and nutritional status, bone density measurement (DEXA scans), magnetic resonance imaging (MRI) and follow-up visits with x-ray and functional assessment. The x-ray controls are standardized to follow the standard guidelines of Hvidovre Hospital and Skåne University Hospital, which at most means three more x-rays for some patients (in total approximately 1mSv with minimal life time risk of cancer). In patients accepting study participation, the researchers are allowed to read hospital files regarding pre- and postoperative health status. Patients will be followed for two years after inclusion. Analysis of hormonal status, health profile and bone density are compared to a standard population. Risk factor analysis will be performed, regarding the risk of sustaining a hip fracture per se as well as the risk of complications and re-operations after hip fracture treatment.

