## **1.b. Association between fracture type, fracture trauma type and bone mineral density**

*First author:* [name]

*Co-authors:* (in random order) [name]; [name], [name]; [name], [name]; [name].

*Last author:* [name]

*Study design:* Prospective multi-center cohort study

*Participants:* Approx. 200 individuals aged 18-60 years

*Exposure:* Acute, non-pathological hip fracture (intra- and extracapsular) regardless of trauma level

*Study groups:* High and low bone mineral density; high and low trauma injuries.

*Aim:*

1. Analysis of association between bone mineral density at the time of hip fracture (DXA scan) and fracture type.

Statistical analysis of categorical data using Chi-square test.

2. Analysis of association between trauma type and fracture type.

Statistical analysis of categorical data using Chi-square test.

*Collected variables in the prospective study:*

Fracture pattern (femoral neck fracture – undisplaced and displaced; basocervical fracture; trochanteric fracture – stable and unstable; subtrochanteric fracture)

Type of trauma (other than low-energy, low-energy)

DXA scan at the time of the fracture

For adjustment:

Gender, age, BMI

Comorbidity, medication

Diet

Abuse – alcohol, drugs, tobacco, anabolic steroids

Socioeconomics (working capacity, type of living)

Fracture history (own and first-hand relatives)

Laboratory tests including hormonal status

Physical / functional level prefracture (New mobility score and others)

Health-related quality-of-life prefracture

*Hypotheses:*

There is no association between low BMD and displaced/unstable hip fracture

There is no association between higher trauma energy and displaced/unstable hip fracture.

There is an association when both low BMD and higher trauma energy exists and displaced/unstable hip fracture.

*Perspective/clinical relevance:*

To understand the interaction between trauma energy level and bone strength (as measured by DXA) and fracture type.

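### SAP 1.a Aim 1 compares patients aged 18-60 with separately assembled middle-aged controls and states no handling of age or sex, nor a BMD scale, so the contrast may be confounded in an unknown direction

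*SAP*

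**What the plan says.** SAP 1.a defines the patients as "Approx. 200 individuals aged 18-60 years" and the control group as "Cohorts of middle-aged, non-fractured individuals with DXA measurements at Odense and Skåne University Hospital". The two groups are thus described by different age terms. The controls' age range, sex mix and number are not stated.

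Aim 1 compares BMD at the time of fracture, and those osteoporosis risk factors that are available in the controls. The method line is "Statistical analysis of categorical data using Chi-square test". The first hypothesis that this comparison serves is "There are differences in BMD and risk factors when comparing the hip fracture group with a standard control group".

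Gender, age and BMI appear in 1.a only among the collected variables. In 1.b the same three head a list introduced by "For adjustment".

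The Protocol adds little. Its Overall Aim speaks of "hormonal status, bone density and health profiles in comparison to a standard population". Material and Method says "Analysis of hormonal status, health profile and bone density are compared to a standard population" and "Risk factor analysis will be performed, regarding the risk of sustaining a hip fracture per se". Neither statement mentions age or sex adjustment.

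**The concern.** Aim 1 contrasts two groups that were assembled separately, so nothing in the design makes them alike in age or sex. If BMD depends on both (assumed here; the documents give no figures), an unadjusted contrast measures fracture status plus whatever age and sex gap exists.

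The direction depends on facts that the documents do not give. Older controls would tend to hide a real deficit in patients, or make patients appear to have higher BMD. Younger controls would do the reverse. A different sex mix can push either way and can add to or offset the age effect. Smoking, BMI and the other risk factors may be confounded too, in directions not examined here.

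At stake is the answer to 1.a's first hypothesis, and with it the sub-study's stated purpose of identifying patients with an underlying cause for an early hip fracture.

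**Working it through.** The plan has no figure to reproduce: it states no effect size, alpha, power or control number. The following is an illustration for BMD only; risk factors were not simulated.

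**From the documents.** About 200 cases aged 18-60; chi-square test.

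**Assumed.** 400 controls; two-sided 5% level; case ages with mean 48 and 20% under 40; BMD with SD 1 within age and sex, falling 0.01-0.04 SD per year after age 30; women 0.5 SD lower; half women in both groups unless stated; low BMD defined as at least 1 SD below the young mean of a half-female population, one cut-off for both sexes; true deficit 0.3 SD or none.

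**Step 1: size of the bias.** Crude difference ≈ true difference + slope × (mean control age − mean case age). Controls spread evenly over 45-65 or 50-60 average 55 years, a gap of 55 − 48 = 7 years.
- Slope 0.01: −0.30 + 0.01 × 7 = −0.23 SD.
- Slope 0.04: −0.30 + 0.04 × 7 = −0.02 SD.

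Controls aged 40-60 average 50, a gap of 2 years, so the shift is only 0.02-0.08 SD.

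**Step 2: effect on the crude chi-square** (2000 simulated data sets per scenario). Power for a true deficit of 0.3 SD:

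| Controls | slope 0.01 | 0.02 | 0.03 | 0.04 |
|---|---|---|---|---|
| 45-65 | 49.5% | 31.6% | 14.2% | 4.1% |
| 50-60 | 51.6% | 32.4% | 13.3% | 4.8% |

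Across repeated runs, matched ages gave about 67-74% and controls aged 40-60 about 50-65%. With no true difference and controls aged 45-65 or 50-60, the test rejects in 8-9% of data sets at slope 0.01 and in 18-65% at 0.02-0.04. At least 90% of these rejections show higher BMD in patients.

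**Step 3: sex mix alone** (ages matched, 50% women among cases). With 70% women in controls, the control mean falls by 0.20 × 0.5 = 0.10 SD, and power drops to 39-40%. With 30% women in controls and no true difference, the test rejects in 14-16%, nearly all falsely showing lower BMD in patients.

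**Step 4: closed-form check, including younger controls.** Take 200 per group, a mean of −0.3 SD for non-fractured people of the patients' age, and low BMD below −1. With a 0.3 SD deficit, cases have Φ(−0.40) = 0.345 low. Controls of the same age have Φ(−0.70) = 0.242, and power is 62%. Controls 5 years older at 0.3 SD per decade have Φ(−0.55) = 0.291:
- difference 0.0534, pooled proportion 0.318
- null SE = √(2 × 0.318 × 0.682 / 200) = 0.0466; threshold 1.96 × 0.0466 = 0.0913
- power = Φ((0.0534 − 0.0913) / 0.0465) = Φ(−0.81) = 21%.

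At 10 years older the deficit cancels exactly (0.345 in both groups). If controls are younger and there is no true deficit, a false deficit appears in 11-42% (5 years) or 29-92% (10 years) for losses of 0.2-0.5 SD per decade.

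**Step 5: after adjustment.** In the scenarios with controls aged 45-65 or 50-60, the age- and sex-adjusted difference stays at −0.30 SD and false rejections are 4-6%. Logistic regression on the same low-BMD outcome has 62-68% power, and linear regression on BMD 83-87%. The logistic figure is the like-for-like comparison; the further gain comes from not dichotomising BMD.

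**Step 6: dependence on the scale.** If low BMD is defined on a perfectly calibrated age- and sex-specific scale, the unadjusted chi-square has about 64-71% power and 4-6% false rejections, whatever the control ages.

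**The case against.** Four points on the other side have force.

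- **Scale.** 1.a names no BMD unit, reference or cut-off. Step 6 shows that age- and sex-specific Z-scores would largely remove the BMD problem. This stands, although perfect calibration is optimistic and Z-scores do nothing for the risk factors.
- **Scope of the chi-square line.** It covers categorical data. BMD is continuous, and groups of high and low BMD are named in 1.b, not in 1.a. The dichotomised analysis simulated here is therefore one reading. This stands; it also means that no method is stated for continuous BMD.
- **Brevity of the SAP.** 1.b also names only a chi-square test, yet lists adjustment variables, so the chi-square line is not a full account of what is intended. A reader might infer that 1.a plans a crude analysis only. The documents support just that no adjustment is stated.
- **Descriptive study.** The Protocol calls the study mainly descriptive and gives no power calculation. This tempers the power figures, but a descriptive contrast between groups is confounded in the same way, and 1.a states a hypothesis and a test.

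A reader might also infer that the controls are older and that the analysis will therefore hide a BMD deficit. Nothing in the documents shows this. The Protocol's Background notes rising incidence in women around 50, so the patients may be mostly middle-aged themselves.

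**Conclusion.** The concern holds as a gap in specification with a real risk of confounding. For Aim 1 the text supplied states no handling of age or sex, no description of the controls beyond a phrase, and no BMD scale.

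Neither the size nor the direction of the bias can be determined from the documents. The low power figures (4-32%) need controls about 7 years older on average, an age slope of at least 0.02 SD per year, and an absolute cut-off shared by both sexes. With controls aged 40-60 the loss is modest. With similar age and sex mix, or well-calibrated Z-scores, the harm to the BMD comparison is small. The point should be fixed because the remedy is cheap and serves the first hypothesis of 1.a, not because a particular wrong result has been shown to be likely.

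**What to change.** In SAP 1.a Aim 1:

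1. Make the main estimate the case-control difference adjusted for age and sex, with a confidence interval: linear regression for BMD and BMI, logistic regression for low BMD and categorical risk factors. Controls matched on age and sex, or age- and sex-specific Z-scores for BMD, are acceptable alternatives; with Z-scores the risk factors still need adjustment.
2. Keep the chi-square test as a crude description.
3. Name the BMD scale and any cut-off.
4. Report the controls' age range, sex mix and number.
5. Add a sensitivity analysis limited to the ages that the controls cover.

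**Cost.** SAP wording and slightly more analysis. No new patient data are needed, provided the control records hold age and sex (assumed).

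**Downsides.**
- The adjusted result extrapolates for cases outside the control ages. In a check with BMD flat to age 50 and then falling 0.03-0.06 SD per year, it was off by up to 0.06 SD with linear age and 0.04 SD with an age spline, against about 0.02 SD at most in the age-limited analysis.
- On the assumed case ages, the age-limited analysis drops 20%, 33% or 51% of cases if controls start at 40, 45 or 50. Its power for 0.3 SD is then 87-90%, 84-85% or 75-79%.
- Controls of one sex only would give no direct comparison for the other sex.

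### SAP 1.a states two compound hypotheses with no primary comparison, and a chi-square test is the only analysis given for an aim it calls descriptive

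*SAP*

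**What the plan says.** SAP 1.a has two aims and two hypotheses.

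- Aim 1 compares BMD and risk factors between fracture patients and control cohorts. The risk factors are described as "basic risk factors for osteoporosis (BMI, smoking, etc. = variables accessible in the control groups"), so the list is left open.
- Aim 2 reads "Descriptive analysis of other relevant factors in a young hip fracture cohort". It names no comparison group.
- Under each aim stands the same single line on method: "Statistical analysis of categorical data using Chi-square test".
- Hypothesis 1 is "There are differences in BMD and risk factors when comparing the hip fracture group with a standard control group".
- Hypothesis 2 is "Within the hip fracture group; different levels of BMD are associated with comorbidities, hormonal status and life style factors".

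The variable list includes bundled lines such as "Abuse – alcohol, drugs, tobacco, anabolic steroids" and "Laboratory tests including hormonal status"; the Protocol (Recorded data) breaks the second into many analytes under eight purposes. Section 1.a gives no primary variable, significance level, number of tests or rule for multiple testing.

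The Protocol (Material and Method) calls the study mainly descriptive and gives that as the reason for having no power calculation. The same section also promises a risk factor analysis, both for sustaining a hip fracture and for complications and reoperations.

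**The concern.** A hypothesis that joins BMD with an open set of risk factors, or BMD level with three families of factors, has no defined way to fail. If one variable reaches nominal significance and the rest do not, the authors can still report the hypothesis as supported, and nothing fixed in advance says otherwise. The chance that at least one variable does so by luck grows with the number examined, and that number is not fixed.

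Aim 2 has a separate problem. A descriptive aim is answered by how common a factor is and how precisely that is known. A chi-square p-value supplies neither, and the aim names nothing to test against.

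The section's stated clinical purpose is to recognise patients with an underlying cause and, where suitable, to start prevention. Readers will therefore take the factors it names as leads for practice, and they need to know which result was planned as decisive and which are leads only.

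**Working it through.** The plan states no number of tests, significance level or error rate, so it has no figure of its own to reproduce. The calculation rests on counts inferred from the lists and on an assumed two-sided level of 0.05.

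**Inputs**

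- Cases: about 200 (SAP 1.a, Participants). The size of the control cohorts is not given.
- Hypothesis 1: BMD, BMI, smoking and an open remainder. Assumed 3 to 8 tests.
- Hypothesis 2: assumed 10 to 13 tests. One count within that range is 12: ASA, Charlson, parathyroid hormone, thyroid tests, sex hormone, BMI, diet, alcohol, drugs, tobacco, anabolic steroids and physical activity. Thyroid tests count once and testosterone/estradiol once, following the purposes in the Protocol's laboratory list.
- Whole variable list of 1.a, without DXA and laboratory tests: gender, age, BMI (3) + comorbidity, medication (2) + diet (1) + abuse (4) + socioeconomics (2) + fracture history (2) + fracture pattern, trauma type (2) + function (1) + quality of life (1) = 18. Adding the Protocol's 8 laboratory purposes gives 26. A range of 15 to 25 therefore stands for a reading in which most listed items are tested.

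**Chance of at least one false finding, independent tests, all nulls true:** 1 − 0.95^k

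| Reading | k | Result |
|---|---|---|
| Hypothesis 1 alone | 3 to 8 | 14% to 34% |
| Hypothesis 2 alone | 10 to 13 | 40% to 49% |
| Hypothesis 2, count above | 12 | 46% |
| Most listed items | 15 to 25 | 54% to 72% |

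The result passes 50% when k exceeds ln 0.5 / ln 0.95 = 13.5, that is, from 14 true-null tests.

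**Correlated tests** (equicorrelated normal statistics, |Z| > 1.96, 400,000 simulations, all nulls true)

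| Correlation | k = 15 | k = 25 |
|---|---|---|
| 0.2 | 49.7% | 66.3% |
| 0.3 | 45.7% | 60.6% |
| 0.5 | 36.3% | 46.8% |

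**Some effects real.** Only true nulls can give a false positive. With 12 true nulls, whether out of 15 or out of 25, the result is 1 − 0.95^12 = 46%. With 20 true nulls out of 25 it is 64%.

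**Other significance level.** At 0.01, 15 tests give 14% and 25 give 22%.

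**Precision for Aim 2** at n = 200, 95% CI half-width = 1.96 × √(p(1 − p)/200)

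- p = 0.50: 1.96 × 0.0354 = 0.069, about ±7 points.
- p = 0.05: 1.96 × 0.0154 = 0.030, about ±3 points.

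**The case against.** The strongest reply is that this is a cohort the Protocol calls mainly descriptive, and that the error-rate figures come from outside the plan. Much of that is right, and it rules out several stronger readings.

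- **That a false finding is more likely than not.** A reader might infer this from the upper figures. It needs a 5% level, which the section does not state, and at least 14 independent true nulls. Neither hypothesis alone clearly reaches 14. At 15 tests the figure falls below 50% with a correlation of 0.2 or with three real effects. The Protocol's Background reports hormonal deficiency, smoking and alcohol abuse as known risk factors, so a setting with no true effects does not fit the study's own premise.
- **That every listed variable gets a chi-square test.** The SAP does not say so. The method line covers categorical data only, and Aim 1 is restricted to what the control cohorts hold.
- **That the result would be a false risk factor for fracture.** Hypothesis 2 concerns fracture patients only. A false positive there is a false correlate of BMD. Only the case-control tests of Hypothesis 1 could yield a false fracture risk factor.
- **That Aim 2 will be reported without prevalences or intervals.** Naming a test does not exclude them. The text is silent, and Hypothesis 2 does supply a comparator (BMD level) for some of these variables.
- **That formal multiplicity control is required.** In an exploratory cohort this is a matter of judgement.

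The descriptive label does not answer the rest. The same Protocol section promises a risk factor analysis, and SAP 1.a states hypotheses rather than estimates to be reported. If the work is exploratory, the section should say so.

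**Conclusion.** The point holds in limited form. SAP 1.a has two compound hypotheses that a single significant result could be taken to confirm, with no primary comparison. For its descriptive aim it plans only a test that yields neither a prevalence nor its precision. Both follow from the text and need no simulation.

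The size of the multiplicity problem is less certain. On any of the counts tried at 5%, the chance of at least one false finding is well above the nominal level, but the exact figure depends on assumed counts, independence and the share of true nulls. It should be quoted as a range with those conditions attached.

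The SAP text available is not complete. A general statement on significance level or multiplicity may stand elsewhere; it would soften the error-rate part but would not make the hypotheses in 1.a less compound or give Aim 2 a descriptive method.

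**What to change.** - Name one primary comparison for 1.a: BMD at one prespecified hip site available in both cases and controls, analysed as a continuous variable. The only method now stated is for categorical data, so this analysis has to be written in.
- Label all other case-control contrasts and all within-cohort BMD associations exploratory, and report each as an effect estimate with a 95% CI. False-discovery control within each family is optional.
- For Aim 2, report prevalence with a 95% CI. Keep tests only for the comparisons across BMD level that Hypothesis 2 calls for, and list those variables.
- Replace the open-ended list under Aim 1 with the actual variables held by the control cohorts.

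The cost is SAP wording and no new data collection, provided that the control cohorts have a hip site in common with the cases. The documents do not give the controls' DXA sites, so this must be checked before the primary comparison is fixed. The scientific price is that fewer secondary factors can be claimed as confirmed.

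### SAP 1.a hypothesises that BMD is associated with comorbidity, hormones and lifestyle, but names only an unadjusted chi-square test and leaves the BMD variable, its levels and any age or sex adjustment unspecified

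*SAP*

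**What the plan says.** Under Hypotheses, SAP 1.a states that "Within the hip fracture group; different levels of BMD are associated with comorbidities, hormonal status and life style factors". The aim closest to this is Aim 2, "Descriptive analysis of other relevant factors in a young hip fracture cohort". The method line, the same under both aims of 1.a, is "Statistical analysis of categorical data using Chi-square test".

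Section 1.a does not say how BMD is expressed (g/cm2, T-score or Z-score), at which skeletal site, in how many levels, or where they are cut. It names no regression or stratification. "Gender, age, BMI" stands at the top of the list of collected variables, with no role in the analysis. Section 1.b does mark a covariate list as being for adjustment, although it names no adjusted model. Its study groups include "High and low bone mineral density", again without a cut-off.

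The planned size is "Approx. 200 individuals aged 18-60 years" in the SAP. The protocol says "The projected number of included patients in the study is 200 to 300 individuals" and adds that "The study is mainly descriptive, wherefore power calculations are not considered feasible". Its sentence on risk-factor analysis (Material and Method) concerns the chance of fracturing and of later complications or reoperation. It names no method and does not address BMD within the cohort.

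**The concern.** The cohort covers both sexes and ages 18 to 59. BMD may differ by age and sex, and so may comorbidity, hormone levels and habits. An unadjusted comparison can then report age or sex under another name. Section 1.a exists to find patients whose fracture has a cause that could be acted on, so a false lead and a missed factor both count against it.

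The second problem is one of precision. BMD from a DXA scan is continuous, and a chi-square test can use it only after it has been grouped. Grouping loses information, and a cut-off that is not fixed in advance can be chosen after the results are seen.

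**Working it through.** The documents give no significance level, effect size, SD, cut-off or age-BMD correlation, so there is no planned figure to reproduce. From the documents: n = 200 (SAP 1.a). Everything else below is assumed, with two-sided alpha 0.05 throughout.

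**1. False positives from missing adjustment.** Simulated model with no true link:
- BMD = -r × age + √(1 - r²) × noise, with age and noise standard normal.
- Log-odds of the comorbidity rise by 0.7 per SD of age, and about 35% of patients have it.
- BMD is split at the median and tested by chi-square without continuity correction.

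| r (age-BMD) | Unadjusted chi-square | Age-adjusted linear regression |
|---|---|---|
| -0.2 | 10% | about 5% |
| -0.3 | 17% | about 5% |
| -0.4 | 28% | about 5% |

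Independent repeats gave 16% to 17% in the middle row and 26% to 29% in the last. With Yates' correction the rates are 7%, 13% and 23%.

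A second model let both age and sex act. The chi-square rejected in:
- 5.5% of runs for weak links (correlations 0.1, odds ratios 1.3);
- 9.6% for correlations 0.2 and odds ratios 1.5;
- 33% for correlations 0.3 and odds ratios 2;
- 43% for correlations 0.4 (age) and 0.3 (sex) and odds ratios 2;
- 7.5% when age and sex pulled in opposite directions.

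Regression adjusted for age and sex rejected in 4.4% to 4.8%.

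**2. Which feature causes the false positives?** One run of the first model changed one thing at a time, for r = -0.2, -0.3 and -0.4:
- Unadjusted chi-square on split BMD: 10%, 16%, 26%.
- Unadjusted continuous BMD: 13%, 24%, 39%.
- Age-adjusted logistic regression on split BMD: about 5%.
- Chi-square on BMD fully standardised for the confounders: about 5%.

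The excess comes from the missing adjustment. Splitting BMD does not cause it, and continuous BMD without adjustment makes it worse.

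**3. Information lost by grouping.** For a normal variable cut at proportion p, the fraction kept is φ(z_p)² / [p(1 - p)].
- Median: 0.1592 / 0.25 = 0.637, a loss of 36%. So 200 patients act like 200 × 0.637 = 127.
- 20/80 split: kept 0.490, loss 51%.
- 10/90 split: kept 0.342, loss 66%.
- Tertiles and quartiles (between-category variance): kept 0.793 and 0.861, losses 21% and 14%.
- If a continuous factor such as a hormone level is median-split too: 0.637² = 0.405 kept, loss 59%.

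**4. Power for an assumed 0.4 SD difference with 35% exposed** (70 against 130 patients).
- Continuous: √(1/70 + 1/130) = 0.148; 0.4 / 0.148 = 2.70; power = Φ(2.70 - 1.96) = 77%.
- Median split: share with low BMD Φ(0.26) = 0.603 against Φ(-0.14) = 0.444; check 0.35 × 0.603 + 0.65 × 0.444 = 0.50. Difference 0.159, standard error 0.5 × 0.148 = 0.074, ratio 2.14; power = Φ(0.18) = 57%.
- Simulation gave 76% to 77% and 55% to 57%; with Yates' correction the chi-square falls to 51%.

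**The case against.** The best defence is that the SAP assigns the chi-square to categorical data, under an aim it calls descriptive, in a study the protocol calls mainly descriptive. No sentence ties the BMD hypothesis to that test. A reader might infer that the plan requires BMD to be cut and tests the hypothesis only in that way. The text does not go so far: analysis of continuous BMD is unspecified, not excluded. That part stands. The descriptive label does not close the gap, because 1.a states an association hypothesis, speaks of levels of BMD and names one significance test.

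A reader might also infer that a fixed share of the information, about a third, is thrown away. That holds only for a two-level split near the median, and the levels are undefined.

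A third tempting reading is that the chi-square or the cut-off itself produces the false positives. The one-at-a-time comparison shows that it does not.

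Finally, age- and sex-matched Z-scores would largely remove the age and sex bias without any model. This is correct, so the bias is conditional on the metric. The SAP does not choose one, and absolute BMD or T-scores would leave the bias in place.

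**Conclusion.** The point holds as a gap in specification with two distinct consequences. Missing adjustment can inflate false positives, to about 10% to 28% against about 5% in the age-only scenarios. The inflation is small if the links with age and sex are weak or opposed, and largely absent if matched Z-scores are used. Grouping BMD costs precision: 36% of the information for a median split, 14% to 66% for the other single groupings of BMD examined. Power is about 56% against 76% in the example. All these sizes rest on assumed inputs; the true size cannot be calculated from the documents.

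The change should be made because it bears on a stated hypothesis and is cheap. Data collection is unaffected.

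**What to change.** In SAP 1.a, Aim 2:
- Name the skeletal site and analyse BMD as a continuous variable by linear regression on each factor.
- Adjust for age and sex as the common covariates, with study site optional. Moving to continuous BMD without this adjustment is not enough.
- Report differences in BMD with 95% confidence intervals.
- Keep BMI and menstrual status for sensitivity analyses. BMI may lie on the pathway from a comorbidity or habit to BMD, and menstrual regularity is close to being part of the hormonal exposure. Routine adjustment could remove the association being sought.
- If high and low groups are kept for display, fix the cut-off before the data are analysed.
- Label the analysis exploratory.

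Age, sex, BMI, menstrual regularity and DXA results are already recorded. The cost is a few lines of SAP text and slightly more analysis work.
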